10. Observer measurements will be recorded simultaneously by the observers on separate sheets. They will be checked immediately by the nurse supervisor and, if they differ by more than 4 mmHg, they will be taken again. Observers will be blinded from each other's measurements and from the device measurements.
11. Starting with the observers, the nurse supervisor will record the measurements sequentially by the supervisor, alternating between observers and the supervisors' reading of the device in the order BPA, BPB, BP1, BP2, BP3, BP4, BP5, BP6 and BP7 on Form 2.
12. **The nurse supervisor** will take a picture of the device measurements and those photographs will be emailed to the research assistant.
13. On a separate sheet, **the nurse supervisor** will keep a running total of the number of subjects recruited in the Low (LL and L), Medium (M), and High (H and HH), ranges for SBP (Box 219) and DBP (Box 220) on Form 2.
14. If any of the following occur during the study, **the nurse supervisor** will circle the appropriate item in Box 287 on Form 2 and exclude the subject:
 - Circle *Arrhythmias* if the subject is not in sinus rhythm throughout the study.
 - Circle *Device failure* if the device fails to record a measurement after three successive attempts.
 - Circle *Poor quality sounds* if the Korotkoff sounds are difficult to auscultate, regardless of the reason.
 - Circle *Observers disagreement* if the observers differ by more than 4 mmHg twice in the same subject.
 - Circle *Other* if the subject does not complete the study for any reason other than those listed and record the reason in Box 288.
15. In the event that an abnormal blood pressure reading is detected (e.g. if the blood pressure is outside clinically normal range for a specific client), one of the observers will

re-take the blood pressure to determine if the abnormal reading is accurate. If the abnormal blood pressure measurement is accurate, the **nurse supervisor** will take appropriate action as directed by professional standards. The abnormal blood pressure data will be recorded on Form 2.

Data Checking

During the data collection process, researchers will check the data daily to ensure the following as per the ESH-IP (O'Brien et al., 2010):

1. Ensure that the difference between the range with the highest count and lowest count does not exceed 19.

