2. Ensure the overall systolic blood pressure is within the range of ≤ 100 to ≥ 170 mmHg and the overall diastolic blood pressure is within the range of ≤ 50 to ≥ 120 mmHg.
3. If the participants have a blood pressure outside the range of 90–180mmHg for systolic blood pressure and 40–130mmHg for diastolic blood pressure, only a maximum of 4 blood pressures readings outside of this range can be included in the analysis.
4. Ensure there are approximately 26-31 participants in each of the 3 blood pressure ranges (low blood pressure (systolic: 0-129, diastolic: 0-79), medium blood pressure (systolic: 130-160, diastolic: 80-100) and high blood pressure (systolic: 161 or higher, diastolic: 101 or higher)).

Data Analysis

[figure not shown]
The profile of the study participants will be described based on a demographic analysis conducted on data collected from the subject data form from the ESH-IP (**Appendix M**).

All collected data on Forms 1 and 2 will be sent to the researchers at the SE Research Centre, who will consolidate the data from the Forms 1 and 2 and analyze the data as specified in Form 3, the Study Results form from the ESH-IP (**Appendix N**) (O'Brien et al., 2010).

In order to pass the validation process, the device must pass both parts 1 and 2 based on the accuracy criteria table (**Appendix O**).

Plots

These are mean-difference plots, and the plots modelled from the data collected should be exactly as shown in the example plots below.

The x-axis of these plots represents blood pressures in the systolic range 80mmHg–190mmHg and the diastolic range 30 mmHg–140 mmHg. The y-axes represent errors from – 30mmHg to +30mmHg. Horizontal reference lines will be drawn at 5mmHg intervals from +15mmHg to – 15 mmHg. The mean of each device pressure and its corresponding observer pressure will be plotted against their difference with a point. Differences greater than 30mmHg will be plotted at 30 mmHg. Differences less than – 30mmHg will be plotted at – 30 mmHg. The same scales will be used for both SBP and DBP plots. Where points are superimposed, these will be indicated either by proportionately larger points or by different symbols.

5. Confidentiality and security of data

Electronic data

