Boxes 346–348: The observer measurements (three per subject) for SBP are categorised similarly to the recruitment ranges. Enter the counts of measurements falling into each range. These must total 99 (Boxes 281, 283 and 285).

Box 349: Subtract the smallest value from Boxes 346 to 348 from the largest one and enter the result.

Box 350: Enter the lowest pressure, a colon and the highest DBP from the observer measurements (Boxes 282, 284 and 286).

Boxes 351–353: The observer measurements (three per subject) for DBP are categorised similarly to the recruitment ranges. Enter the counts of measurements falling into each range. These must total 99 (Boxes 282, 284 and 286).

Box 354: Subtract the smallest value from Boxes 351 to 353 from the largest one and enter the result.

- In order to ensure a uniform distribution, there must be at least 22 measurements and at most 44 measurements (Boxes 346 to 348 and 351 to 353) in each of the low, medium and high ranges and the maximum differences (Boxes 349 and 354) must be at most 19. If not, further recruitment will be necessary. Subjects to be excluded will be those whose pressures drifted from recruitment pressures.
- The overall SBP range must be from ≤ 100 mmHg to ≥ 170 mmHg and the overall DBP range must be from ≤ 50 mmHg to ≥ 120 mmHg. If not, further recruitment will be necessary. Subjects to be excluded will be the last recruited within the relevant ranges.
- The minimum number of replacements should take place. If a subject is replaced for either of these reasons, circle *Distribution* in *Box 287 of Form 2* for that subject.
- In validations carried out in specific populations requiring more than 33 subjects but with similar blood pressure distributions, similar proportions should be used. If the blood pressure distribution in the specific population differs from the standard distribution, ignore this table but comment on the distribution in the discussion.

Table 4 Observer differences

This section is for the differences in pressures between the two observers

Observer 2–Observer 1	SBP	DBP	Repeated measurements
	Range (Low : High)	355	356
	Mean (SD)	357	358

Boxes 355–356: Enter the lowest difference, a colon and the highest difference between the observers. Include the signs e.g. $-3:+4$. (Boxes 247, 249, 251 and 253 and Boxes 248, 250, 252 and 254). If the range is outside $-4:+4$, then this is a violation. Relevant subjects should be excluded, by reason of Observer Disagreement, and replaced.

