Appendix O – International Protocol Accuracy Criteria

ESH International Protocol 2010			
Sequential Measurements			
IP Grading Part 1 - Minimum Requirements (at least 255 pairs of individual measurements)			
N	≤ 5 mmHg	≤ 10 mmHg	≤ 15 mmHg
Two of	188	224	247
All of	167	209	240
IP Grading Part 2 (85 subject mean pressures)			
N	$2/3 \leq 5$ mmHg		$0/3 \leq 5$ mmHg
At least	62		
At most			8
Recruitment Ranges (n = 85)			
SBP		DBP	
mmHg	Subjects	mmHg	Subjects
90*...129	26 – 31	40*...79	26 – 31
130...160	26 – 31	80...100	26 – 31
161...180*	26 – 31	101...130*	26 – 31
*	Altogether, up to 4 recruitment pressures are permitted to be outside these limits.		
Test Measurement Distribution			
SBP		DBP	
mmHg	Measurements	mmHg	Measurements
≤ 100	≥ 3	≤ 50	≥ 3
< 130	57 – 113*	< 80	57 – 113*
130...160	57 – 113*	80...100	57 – 113*
> 160	57 – 113*	> 100	57 – 113*
≥ 170	≥ 3	≥ 120	≥ 3
*	The difference between the maximum and minimum of these 3 counts for SBP and, separately, for DBP, must be less than or equal to 19.

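### The limit of 19 on the spread of range counts stayed at its 99-reading value when the rest of Appendix O's distribution table was scaled to 255 readings, so the printed 57–113 can never bind

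*Combined protocol and SAP*

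**What the plan says.** Form 3 is the source form, written for 33 subjects and 99 readings per pressure. Its Table 3 notes say that in each of the low, medium and high ranges "there must be at least 22 measurements and at most 44 measurements", and that "the maximum differences (Boxes 349 and 354) must be at most 19". If either rule is broken, more subjects are recruited and those whose pressures moved away from their recruitment values are excluded, with as few replacements as possible. For larger samples the notes add: "In validations carried out in specific populations requiring more than 33 subjects but with similar blood pressure distributions, similar proportions should be used".

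Appendix O gives the rules for 85 subjects. Its Test Measurement Distribution table prints 57–113 readings per range. The footnote to those limits says that the difference between the highest and lowest of the three counts "for SBP and, separately, for DBP, must be less than or equal to 19".

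Data Checking mixes the two scales. Item 1 reads "Ensure that the difference between the range with the highest count and lowest count does not exceed 19", without saying what is counted. Item 4 reads "Ensure there are approximately 26-31 participants in each of the 3 blood pressure ranges", which is the 85-subject quota.

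Data Analysis tells the researchers to "analyze the data as specified in Form 3, the Study Results form from the ESH-IP". It names Appendix O as the basis for passing Parts 1 and 2, but does not say which document governs the distribution limits.

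**The concern.** The footnote and the limits it qualifies belong to different sample sizes. Two rules meant to work together no longer do: one has become much stricter relative to the number of readings, and the other is inert. The spread limit triggers action on who stays in the analysis set, so its value matters in practice. An unintended tight limit means avoidable recruitment, and removal of subjects who have already been measured.

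The consequence of a breach is also unsettled. The Table 3 notes treat it as a reason to recruit further. The note under Form 3 Table 5 makes a pass conditional on every protocol requirement being met. What follows if a breach is not remedied is not stated, so staff need one clear limit.

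**Working it through.** **Inputs.** Form 3: 33 subjects, 99 readings, 22–44 per range, spread at most 19, quotas 10–12, pass counts 73/87/96, 65/81/93, 24 and 3. Appendix O: 85 subjects, 255 readings. Scaling factor: 255/99 = 85/33 = 2.5758.

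**Reproducing Appendix O.** Multiply each Form 3 figure by the factor and round.

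| Item | Form 3 | Scaled | Appendix O |
|---|---|---|---|
| Part 1, two of | 73 / 87 / 96 | 188.03 / 224.09 / 247.27 | 188 / 224 / 247 |
| Part 1, all of | 65 / 81 / 93 | 167.42 / 208.64 / 239.55 | 167 / 209 / 240 |
| Part 2 | 24 / 3 | 61.82 / 7.73 | 62 / 8 |
| Quotas | 10–12 | 25.76–30.91 | 26–31 |
| Per-range limits | 22–44 | 56.67–113.33 | 57–113 |
| Spread limit | 19 | 48.94 | **19** |

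The minimum of 3 readings at each extreme also fits. Form 3 prints no count there, but a rule such as "The overall SBP range must be from ≤ 100 mmHg" needs at least one reading, and 1 × 2.5758 = 2.58. As a share of readings, 19/99 = 19.2%, 19/255 = 7.5% and 49/255 = 19.2%.

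**What the spread rule alone allows.** If three counts total N and differ by at most d, each lies between (N − 2d)/3 and (N + 2d)/3.

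- N = 99, d = 19: 20.33 to 45.67, so 21–45. The limits 22–44 bind.
- N = 255, d = 19: 72.33 to 97.67, so 73–97. The limits 57–113 cannot bind.
- N = 255, d = 49: 52.33 to 117.67, so 53–117. The limits 57–113 bind again. With d = 48 the range is also 53–117.
- N = 279, d = 19 (93 subjects, the quota ceiling of 3 × 31): 80.33 to 105.67, so 81–105. The limits 57–113 still cannot bind.

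Enumerating all ordered count triples confirms this. At 255 readings, 2,437 triples meet 57–113. Of these, 379 (16%) also meet 19, and those 379 are every triple that meets 19 at all; 2,269 (93%) meet 49. At 99 readings, 361 of the 397 triples within 22–44 (91%) meet 19.

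**Room left for drift.** The quotas allow 27 ordered splits of 85. Six of them, the orderings of 26/28/31, give 78/84/93 readings if nothing drifts: a spread of 15, leaving 4. In the 33-subject form the largest no-drift spread is 3 × (12 − 10) = 6, leaving 13.

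From 28/29/28 the readings are 84/87/84. If k readings move from high to medium, the spread is (87 + k) − (84 − k) = 3 + 2k.

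- Limit 19: first broken at k = 9 (spread 21), which is 9 of 84 readings.
- Limit 49: first broken at k = 24 (spread 51), which is 24 of 84.
- Limit 19 from 33/33/33: the spread is 2k, first broken at k = 10, which is 10 of 33.

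**Illustration only.** The documents give no drift figures. I assumed entry pressures uniform within range, normal drift with between-subject SD 3 or 5 and within-subject SD 3 or 4, a fixed split and a single check. For SBP from 28/29/28, the limit of 19 is broken in about 11–23% of simulated studies with no mean fall and about 49–61% with a 2 mmHg fall. At 49 both are under 1%. Recruiting 26/28/31 (low/medium/high) instead changes the 2 mmHg figure to about 16–26%.

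**The case against.** The strongest reply is that redundancy is not contradiction. Counts of 85/85/85 satisfy everything, a tighter evenness rule is conservative, and even in Form 3 the per-range limits removed only 18 of 379 triples (379 − 361). All of that is true. The plan can be carried out as written, and a reader who inferred that the limit is impossible to meet would be wrong.

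Second, 19 may be deliberate. Appendix O's other footnoted cap, 4 recruitment pressures outside the limits, also keeps its 33-subject value (proportionally 10.3), which would fit caps held fixed on purpose. The scaling sentence in Form 3 is worded for specific populations, so it applies here only by analogy. The protocol also says it is modified by a consensus statement, whose text is not available here. The documents therefore do not prove a slip. But they give no reason for 19, and Appendix O did scale the very limits that this footnote qualifies. The cap of 4 makes no other printed limit redundant; 19 does.

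Third, the simulated rates are fragile. They rest on invented drift, change with the recruitment split, ignore daily checking, and do not model the rule that the counted observer reading is the one nearer the device. The triple counts are not probabilities either. I accept this: neither is a forecast of breaches.

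**Conclusion.** The inconsistency stands on arithmetic from the documents alone. Every other figure in the distribution table fits scaling to 255 readings; the spread limit does not, and it makes the adjacent limits inert. Relative to sample size the rule is about 2.6 times tighter than its source. The firm measures of size are 7.5% against 19.2% of readings, 6 of 27 permitted splits using 15 of the 19 before any drift, and 9 of 84 crossings against 10 of 33.

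Two stronger readings are not supported. One is that a breach fails the study: the Table 3 notes prescribe recruitment and replacement, and the Table 5 note leaves an unremedied breach unclear, no more than that. The other is that the exclusions bias the accuracy result. Removing drifted subjects could favour a device calibrated to a baseline pressure, but nothing in the documents shows that it does. The pass counts are unaffected.

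The likely cost is avoidable recruitment and replacement. This should be corrected before data checking relies on it, but it does not undermine the validation.

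**What to change.** - In the Appendix O footnote and Data Checking item 1, replace 19 with 49 (48 if rounded down). If 19 is intended, state the reason and delete the redundant 57–113.
- In item 1, say that the counts are readings, for SBP and DBP separately. For subjects the quotas already cap the difference at 31 − 26 = 5, so 19 has meaning only for readings.
- In Data Analysis, state that for n = 85 Appendix O governs over the 33-subject and 99-reading figures in both Form 3 and Form 2. This must cover the Form 2 instruction to close recruitment when both range counts exceed 12, which conflicts with quotas of 26–31.
- State what happens if the distribution limits are still breached when recruitment ends.
- Keep reporting the number of subjects removed for distribution, which Form 3 Box 310 already records.

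The cost is one number in two places and a few sentences; no new data are needed. The downside is a slightly less even spread of readings, still held within 57–113.

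A separate point to reconcile: Data Checking item 3 applies the cap of 4 to readings in the analysis, while Appendix O applies it to recruitment pressures.
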